# **18.3** Frequency of analysis

There are no formal analyses planned until after the trial is closed to recruitment. The analysis of the primary endpoint and all secondary endpoints will take place when all participants have been followed up for safety, i.e. 7 days after last trial treatment dose.

A Trial Steering Committee (TSC) will be set up to independently review data on safety, protocol adherence and recruitment. The TSC will review safety data for all participants entered into the trial approximately 6 months into recruitment (or as deemed appropriate by the TSC). Interim reports containing safety data, protocol adherence and recruitment will be presented to the TSC in strict confidence.

### **18.4 Primary Endpoint Analysis**

The average number of patients recruited per month across 3 trial sites over a 12-month period will be summarised, overall and by trial site. The total number of patients recruited will be summarised by month, overall and by trial site.

Summaries will be presented overall by treatment arm, and by recruitment setting and diagnosis.

# 18.5 Secondary Endpoint Analysis

#### 18.5.1 Feasibility

The number of approaches to patients and randomisations in total throughout the randomisation period and per month will be summarised overall and by recruitment setting and diagnosis. The proportion of screened patients who are eligible for randomisation will be presented with corresponding 95% confidence intervals. Reasons for non-eligibility will be summarised. The proportion of eligible patients who are randomised will be presented with corresponding 95% confidence intervals. Reasons for non-eligibility be summarised.

The proportion of participants for whom blinding is maintained will be summarised overall and by treatment arm, and also by recruitment setting and diagnosis, with corresponding 95% confidence intervals. The proportion of participants who became unblinded and the reasons for unblinding will also be presented. The blinding index for each arm will be calculated using the bang blinding method along with 95% confidence interval. The blinding index calculates the difference between the proportion of correct and incorrect "guesses". The blinding index takes values between -1 and 1.

The proportion of participants who remain on study for 28 days, will be summarised overall and by treatment arm, and also by recruitment setting and diagnosis, with corresponding 95% confidence intervals. The proportion of participants who stop treatment early and the reasons for stopping treatment will be presented.

The proportion of participants who would be eligible for dose escalation at 28 days, will be summarised overall and by treatment arm, and also by recruitment setting and diagnosis, with corresponding 95% confidence intervals. Those participants who would have not been eligible for dose escalation will be summarised along with the reason why they were not eligible for dose escalation.

The proportion of participants with missing data for each trial outcome separately will be summarised overall and by arm, at each time point of assessment. Where available, reasons for missing data will be provided.

Treatment compliance will be summarised by the proportion of participants with dose reductions or omissions and total number of missed doses, by treatment arm. Reasons for dose reductions or omissions will also be presented.

Qualitative data will be analysed by the qualitative researcher. A separate analysis plan will be written outlining the proposed analysis.

Health Economic data will be analysed by the Health Economics researcher. A separate analysis plan will be written outlining the proposed analysis.

#### 18.5.2 Activity

Descriptive summaries of average severity of breathlessness over the last 24 hours and at worst, as assessed by NRS score, will be presented overall and by arm at each time point (baseline, days 7, 14, 21 and 28). Change in average and worst 24 hour breathlessness NRS score from baseline will also be presented with corresponding 95% confidence intervals. Average and worst breathlessness/24 hours will also be presented graphically using line graphs.

Differences in average and worst breathlessness/24 hours at day 28 between arms will be estimated using multi-level repeated measures modelling adjusting for NRS score at baseline, days 7, 14 and 21, and for minimisation factors, and incorporating time, treatment, and treatment by time interaction terms. Covariate estimates will be presented with corresponding standard errors. Treatment effect size (change in average and worst breathlessness) will be presented with corresponding 95% confidence intervals.

Mean Chronic Respiratory Questionnaire (CRQ) total score will be summarised with corresponding 95% confidence intervals and presented by treatment arm for baseline, days 14 and 28 by treatment arm. Mean change from baseline will also be summarised.

Mean lower extremity functioning, measured by the Short Physical Performance Battery (SPPB) at baseline and on day 28 will be summarised with corresponding 95% confidence intervals and presented by treatment arm. Mean change from baseline will also be summarised.

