#### 11.1.1 Treatment Regimen

Participants will be randomised to receive either mirtazapine or placebo for 28 days. Participants will be dispensed 42 capsules (15mg per tablet for mirtazapine) at baseline. Participants should take their capsules in the evening.

For participants randomised to receive mirtazapine, the daily dose will be 15mg (one capsule) for the first 14 days; participants will be assessed for possible dose escalation at the trial assessment visit for day 14 and if appropriate, their daily dose will be escalated to 30mg (two capsules) on days 15 through to 28; see section 12.5.2.1 below for further details.xii Where dose escalation is not appropriate, the participant will continue to take a daily dose of 15mg (one capsule) on days 15 through to 28.

For participants randomised to receive placebo the daily dose will be 1 capsule for the first 14 days; participants will be assessed for possible dose escalation on day 14 and if appropriate, their daily dose will be escalated to 2 capsules on days 15 through to 28; see section 12.5.2.1 below for further details.xiii Where dose escalation is not appropriate, the participant will continue to take a daily dose of 1 capsule on days 15 through to 28.

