# 14. Participant-reported measures

The various participant-reported measures (all of which will be administered by the researcher) of symptoms, activity, Quality of Life (QoL) and outcomes used in the BETTER-B Feasibility trial have been selected based on a national consensus statement of a National Cancer Research Institute (NCRI) Group on breathlessness , two systematic reviews of measures of breathlessness , and a study estimating the size of a clinically important difference .

Most of these measures are brief scales, with a total of 70 participant-reported questions (at baseline), which overall (time for the questions and observation) take around 30-45 minutes to complete. This has been found acceptable in other studies . As part of this BETTER-B Feasibility trial we will assess which scales are suitable for a future large-scale trial based on missing data, patient acceptability and time to complete, so that the questions can be kept to a minimum in the future trial.

The participant-reported measures used in the BETTER-B Feasibility trial are:

- Numerical Rating Scale (NRS) for breathlessness: this assesses the severity of breathlessness in the previous 24 hours on a 0-10 numerical rating scale, for average, and worst . It will be administered to participants at baseline and at the assessment calls/visits for days 7, 14, 21 and 28.
- Modified Medical Research Council (mMRC) dyspnoea scale: this assesses the overall level of breathlessness and will be administered to participants at assessment visits for days 14 and 28.
- Chronic Respiratory Disease Questionnaire (CRQ):xxxiii this is a 20 item widely validated health-related quality of life questionnaire. Experiences are rated on 7-point scale ranging 1 (maximum impairment) to 7 (no impairment)  This will be administered to participants at baseline and at the assessment visits for days 14 and 28 .
- EQ-5D-5L: this assesses mobility, self-care, usual activities, pain/discomfort, anxiety/depression according to three levels of severity (1=no problems; 2=some or moderate problems; 3=extreme problems), plus a Visual Analogue Scale (VAS) of current health-related quality of life, scored 0-100. This will be administered to participants at baseline and at the assessment visit for days 28.

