#### 16.2.2 Activity

- **Key Activity endpoint:** severity of breathlessness at the assessment visit for day 28 as assessed by the NRS ("at worst" severity of breathlessness over the last 24 hours).
- Severity of breathlessness at the assessment visits/calls for days 7, 14 and 21, as assessed by NRS (average and "at worst" severity of breathlessness as assessed over the last 24 hours).
- Lower extremity functioning as assessed by the Short Physical Performance Battery (SPPB)  at the assessment visit for day 28.
- Opioid medication: at the assessment visits/calls for days 7, 14, 21 and 28.

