# 17. Statistical Considerations

#### Sample size and planned recruitment rates

As the trial is designed to assess the feasibility of conducting a future definitive large-scale trial, a formal power calculation is not considered appropriate as effectiveness is not being formally evaluated.

The future large-scale trial would be designed to detect a minimum clinically important effect size of 0.5 in NRS (or a 1 point change) . With 90% power testing at the 5% two-sided significance level, approximately 90 participants per arm would be required. This sample size calculation will be revisited based on the observed variability of the primary outcome in this feasibility trial. It is expected that attrition rates will be approximately 20%, however this will be assessed within this feasibility trial. Assuming a 20% attrition rate, the future trial would require approximately 230 participants in total.

Feasibility of recruitment to a future large-scale trial of the same design will be concluded if the trial is able to recruit an average of 5 patients per month over a 12-month period, equivalent to approximately 60 patients, based on 3 recruiting sites. This equates to 1-2 patients per month, per site. The sites taking part in the feasibility trial are representative of those sites which would be involved in the future larger trial. Assuming 11 sites open to recruitment in the future trial, recruiting 1-2 patients per month each, this would mean a 230-participant trial would be expected to recruit in approximately 18 months to allow for the setup and initiation of all sites.

For this feasibility trial we plan to recruit approximately 60 patients in total (i.e. 30 patients to each treatment arm) from 3 sites in the UK over a 12-month period. Guidance on pilot study design by Browne et al  state that at least 30 patients should be included to estimate a parameter for future sample size calculation . In order to estimate the expected variability of the future large-scale trial's primary outcome measure of breathlessness ("at worst") at day 28 in the mirtazapine arm, 30 participants are required. As the future trial will be randomised, this equates to a total of 60 participants required, with 1:1 randomisation.

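### The day-28 breathlessness model lists on-treatment NRS scores (days 7, 14, 21) as covariates, which contradicts its own repeated measures structure and, taken literally, shrinks the treatment effect by an unknown amount

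*Protocol*

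**What the plan says.** Protocol section 18.5.2 (Activity) sets the target: "Differences in average and worst breathlessness/24 hours at day 28 between arms will be estimated". The method is "multi-level repeated measures modelling adjusting for NRS score at baseline, days 7, 14 and 21, and for minimisation factors", and the model is described as "incorporating time, treatment, and treatment by time interaction terms". The resulting effect, for both average and worst breathlessness, is to be reported with a 95% confidence interval.

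Three other places fix what those scores are:

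- Section 14, on the NRS: "It will be administered to participants at baseline and at the assessment calls/visits for days 7, 14, 21 and 28".
- Section 11.1.1, on dosing in the mirtazapine arm: "the daily dose will be 15mg (one capsule) for the first 14 days". Dosing therefore precedes the day 7, 14 and 21 assessments.
- Section 16.2.2 lists as an activity endpoint: "Severity of breathlessness at the assessment visits/calls for days 7, 14 and 21, as assessed by NRS". The same section makes worst breathlessness at day 28 the key activity endpoint.

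**The concern.** Adjusting for baseline NRS is sound, because treatment cannot have changed it. The scores at days 7, 14 and 21 are different: if mirtazapine works, part of its effect is already in them. Holding them fixed removes that part from the day-28 comparison. Day 14 carries a further complication, since worst NRS at that visit also feeds the dose-escalation assessment (section 12.5.2.1). Conditioning on it conditions on a post-treatment value that influences later exposure.

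The sentence also fails as a specification. A repeated measures model with time and treatment-by-time terms needs several post-baseline responses. The covariate list uses up all of them except day 28.

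At stake is the activity estimate. Section 5.4 gives an estimate of likely activity, to inform the large trial's design, as one reason for running the feasibility trial. Section 18.5.2 specifies no other modelled between-arm comparison for the key activity endpoint.

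**Working it through.** The protocol states no figure for this model, so there is none to reproduce. The check has three steps.

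**1. The two possible readings**

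- *Covariates only.* Day 28 is the single response, one row per participant. Time is then constant, and time and treatment-by-time cannot be estimated.
- *Responses as well.* Each day 7, 14 or 21 row has its own value, and values measured at other visits, among its predictors. The treatment term no longer estimates a difference between arms at that visit.

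Neither reading gives the day-28 difference that the sentence names.

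**2. Size of the loss under the covariate reading**

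Let d(t) be the true effect at visit t, with d(baseline) = 0. Let b be the slopes of day-28 NRS on the scores at baseline and days 7, 14 and 21: b = S⁻¹s, where S is the covariance matrix of those four scores and s their covariances with day 28. The fitted treatment coefficient is d(28) − Σ b(t)d(t), so the share lost is Σ b(t)d(t) / d(28).

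The correlation r and the onset profile are assumptions; the protocol gives neither.

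- Exchangeable correlation: every slope is r/(1 + 3r). For a constant effect from day 7 the share lost is 3r/(1 + 3r). At r = 0.5 each slope is 0.5/2.5 = 0.2, so 3 × 0.2 = 60% is lost.
- AR(1) correlation: only day 21 has a non-zero slope, equal to r. A constant effect loses r; linear onset loses 0.75r; onset after day 14 loses 0.5r.

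| Onset (effect at days 7, 14, 21 as a share of day 28) | Exchangeable, r = 0.3 / 0.5 / 0.7 / 0.8 | AR(1), same r |
|---|---|---|
| Constant from day 7 (1, 1, 1) | 47 / 60 / 68 / 71% | 30 / 50 / 70 / 80% |
| Linear over 28 days (0.25, 0.5, 0.75) | 24 / 30 / 34 / 35% | 22 / 38 / 52 / 60% |
| After day 14 (0, 0, 0.5) | 8 / 10 / 11 / 12% | 15 / 25 / 35 / 40% |
| Day 28 only (0, 0, 0) | 0% | 0% |

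**3. Simulation check**

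The setting was 2,000 trials of 30 per arm (section 17), a true effect of −1 point and SD 2. The SD follows from section 17 equating an effect size of 0.5 with 1 point: 1/0.5 = 2. Correlation was exchangeable, and day-28 NRS was regressed on treatment and the listed scores.

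| Setting | Mean estimate, baseline only | Mean estimate, baseline and days 7, 14, 21 |
|---|---|---|
| r = 0.5, constant effect | −0.99 | −0.39 |
| r = 0.7, constant effect | −0.99 | −0.31 |
| r = 0.5, linear onset | −1.00 | −0.70 |
| r = 0.7, linear onset | −1.00 | −0.66 |

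These agree with step 2: 1 − 0.60 = 0.40, 1 − 0.68 = 0.32, 1 − 0.30 = 0.70 and 1 − 0.34 = 0.66. There is little gain in precision to set against the bias. In the first row the standard deviation of the estimates falls only from 0.45 to 0.43.

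**The case against.** The strongest reply is that the authors probably meant an ordinary repeated measures model. The time and treatment-by-time terms make sense only if days 7 to 28 are responses, so the covariate list may be a slip of wording. That is plausible, and it is why the point is a self-contradiction and not proof that a day-28 regression was intended. It does not rescue the text: the list names the on-treatment days beside baseline, and an analyst who follows it fits the wrong model.

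The role of the analysis is limited, and this stands. The primary endpoint is recruitment (16.1), analysis is descriptive with no formal tests (18.1), and activity results do not enter the decision to proceed (6.3.2, 16.2.1). Section 18.5.2 also presents NRS by arm at every visit and change from baseline with confidence intervals, so a reader could notice that the modelled effect looks too small. The report would then hold two conflicting answers.

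Section 18.1 promises a more detailed analysis plan, which was not available here. But the covariate list is a rule the protocol states wrongly, not a detail it leaves open.

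Two stronger readings are tempting, and the documents do not support them:

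- *Most of the effect is adjusted away.* That needs an early, sustained effect with correlation of about 0.5 or more, or gradual onset with high AR(1) correlation. The protocol documents neither, and escalation from day 15 makes a later effect possible.
- *The future trial would be too small because this model's residual variance is too low.* Section 17 says "This sample size calculation will be revisited based on the observed variability of the primary outcome in this feasibility trial", and justifies 30 participants for estimating the variability of worst day-28 breathlessness in the mirtazapine arm. The target difference is a fixed 1 point. Neither this model's residual variance nor its coefficient is said to enter that calculation.

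**Conclusion.** The specification is wrong as written. It contradicts itself on which NRS scores are responses, and read literally it estimates the day-28 effect remaining after the effect seen by day 21 is removed. The bias is towards no effect, provided that visits are positively correlated and earlier effects run in the same direction. Its size cannot be fixed from the protocol: it spans 0 to about 80% over correlations of 0.3 to 0.8, two correlation structures and four onset profiles, all assumed.

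A further consequence is conditional. Under the covariate reading with complete-case fitting, a participant with a day-28 score but a missing day 7, 14 or 21 score would drop out of the contrast. Section 18.5.2 does not say that complete cases will be used.

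The primary endpoint and the decision to proceed are unaffected. The correction is still needed before analysis, because the model does not estimate the quantity it names.

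**What to change.** In section 18.5.2, replace the model sentence with one that states:

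- NRS at days 7, 14, 21 and 28 is the repeated response, with average and worst modelled separately.
- Fixed effects are baseline NRS, categorical time, treatment, treatment-by-time and the minimisation factors.
- Within-participant correlation is handled by a participant random effect or an unstructured covariance.
- The reported result is the treatment contrast at day 28 with its 95% confidence interval.

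Remove days 7, 14 and 21 from the covariate list. Participants who miss an intermediate visit then still contribute their other scores.

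The cost is one sentence in the protocol, with the statistical analysis plan checked for the same wording. No new data are needed, since every score is already scheduled, and nothing changes for sites or participants.

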## 6.3.2 Activity, Quality of Life and Toxicity

To obtain average and worst breathlessness severity estimates (measured using Numerical Rating Scale (NRS)) on day 28 to inform the sample size calculations for the future large-scale trial.

To determine patient eligibility to increase the dose of mirtazapine further at 28 days.

To assess the potential activity and impact on the activity of mirtazapine and quality of life (QoL) for patients with refractory breathlessness using the following tools:

- Breathlessness mastery: Chronic Respiratory Questionnaire (CRQ) and modified Medical Research Council (mMRC) dyspnoea scale  on days 14 and 28;
- Lower extremity functioning: Short Physical Performance Battery (SPPB)  on day 28 ;
- Coping self-belief assessment: Generalized Self-Efficacy Scale (GSES) on day 28;
- Palliative symptoms: Integrated Palliative care Outcome Scale (IPOS) on days 14 and 28;
- Anxiety and depression: Hospital Anxiety and Depression Scale (HADS) on days 14 and 28;
- QoL: EQ-5D-5L on day 28 and Australia-modified Karnofsky Performance Scale (AKPS)  on days 14 and 28;
- Health Economics: Client Services Receipt Inventory (CSRI) on day 28;
- Opioid medication: on days 7, 14, 21 and 28;

To monitor adverse reactions, using the Common Terminology Criteria for Adverse Events (CTCAE) categorisation (v4) , on days 7, 14, 21 and 28, in order to evaluate the toxicity profile of mirtazapine in patients with refractory breathlessness.

If we are able to demonstrate feasibility within this trial, i.e. the ability to recruit an average of 5 patients per month within a 12-month period (approximately 60 patients) then we plan to seek funding to run a larger double-blind, placebo-controlled randomised trial. Secondary outcome measures of feasibility will be assessed to determine whether the design of the future large-scale trial may need to be adapted to improve recruitment or reduce attrition. Physical activity and toxicity outcomes will be used to inform the design of the future trial however they will not be used to inform the decision as to whether or not to proceed to a larger scale trial. The primary aim of the future trial would be to determine whether mirtazapine improves breathlessness in patients with refractory breathlessness compared to placebo, based on breathlessness severity at day 28 as the primary outcome measure.

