# 15. Economic Evaluation

The economic evaluation component of this trial aims to test the feasibility of collecting cost data, with modified CSRI, and quality of life data, with EQ-5D-5L. We will develop the tailored CSRI questionnaire, considering patient understanding and care settings. It will be ideal to collect cost data by formal health care, social care and informer care separately. We will identify difficulties answering CSRI questions, if any, by checking item response rate and reading free text answers to open-ended questions.

We will calculate the summary statistics of formal and informal care costs (and social care costs, if possible) for the last four weeks at baseline and at the assessment visit for day 28.

Finally we will examine the possibility of assessing the cost-effectiveness using outcome measurements (average breathlessness severity measured by NRS for breathlessness, breathlessness mastery measured by CRQ and IPOS and Quality Adjusted Life Years (QALYs) derived from using EQ-5D-5L) at 4 weeks. We will explore if it is possible to produce a cost-effectiveness plane with the results from the cost-effectiveness analysis.

<sup>xxxv HADS copyright © R.P. Snaith and A.S. Zigmond, 1983, 1992, 1994.Record form items originally published in Acta Psychiatrica Scandinavica 67, 361–70, copyright © Munksgaard International Publishers Ltd, Copenhagen, 1983.This edition first published in 1994 by nferNelson Publishing Company Ltd (now GLAssessment Ltd),[name] GL Assessment Ltd is part of the Granada Learning Group.

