#### 16.2.4 Symptoms and Quality of Life

- Coping self-belief assessment as assessed by the General Self-Efficacy Scale (GSES) at the assessment visit for day 28.
- Mobility, self-care, usual activities, pain/discomfort and anxiety/depression as assessed by EQ-5D-5L at the assessment visit for day 28.
- Palliative symptoms as assessed by the Integrated Palliative care Outcome Scale (IPOS) at the assessment visits for days 14 and 28.
- Anxiety and depression as assessed by the Hospital Anxiety and Depression Scale (HADS) at the assessment visits for days 14 and 28.
- QoL as assessed by Chronic Respiratory Questionnaire (CRQ) at the assessment visits for days 14 and 28.

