# 18. Statistical Analysis

# 18.1 General Considerations

Statistical analysis of the main feasibility trial is the responsibility of the CTRU Statisticians. The analysis plan outlined in this section gives a brief description of the statistical analyses which will be carried out at the end of recruitment and trial follow-up. A final, more detailed, statistical analysis plan will be written before any analysis is undertaken. Given that this is a feasibility trial, the analysis will require descriptive statistics rather than any formal hypothesis testing.

Baseline characteristics of patients will be summarised.

Qualitative and Health Economics analyses will be the responsibility of the qualitative researcher and health economist respectively.

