#### 18.5.3 Safety and Toxicity

The number of SAEs, SARs and SUSARs will be summarised descriptively by arm, by causality, seriousness, and body system.

The proportion of participants experiencing each toxicity will be summarised by maximum NCI CTCAE grade experienced over 28 days, by treatment arm.

The change in AKPS and mMRC from baseline to day 14 and 28 will be summarised.

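### The CRQ is named as a measure of breathlessness mastery, but no endpoint or statistical-analysis section specifies a CRQ mastery score

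*Protocol*

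**What the plan says.** The protocol gives the CRQ two roles.

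- **Objective (6.3.2).** One bullet, for days 14 and 28, reads "Breathlessness mastery: Chronic Respiratory Questionnaire (CRQ) and modified Medical Research Council (mMRC) dyspnoea scale".
- **Economic evaluation (15).** The candidate outcomes for the cost-effectiveness exploration at 4 weeks include "breathlessness mastery measured by CRQ and IPOS".
- **Instrument (14).** Of the CRQ: "this is a 20 item widely validated health-related quality of life questionnaire", with items scored 1 to 7. No domains are described. The mMRC is described in the same section as an assessment of the overall level of breathlessness.
- **Endpoint (16.2.4).** "QoL as assessed by Chronic Respiratory Questionnaire (CRQ) at the assessment visits for days 14 and 28". Mastery is not mentioned.
- **Analysis (18.5.2).** "Mean Chronic Respiratory Questionnaire (CRQ) total score will be summarised with corresponding 95% confidence intervals", by arm at baseline, day 14 and day 28, with mean change from baseline. No other CRQ score is named.
- **Analysis of the mMRC (18.5.3).** "The change in AKPS and mMRC from baseline to day 14 and 28 will be summarised".
- **Status of the analysis section (18.1).** "A final, more detailed, statistical analysis plan will be written before any analysis is undertaken". For this trial, "the analysis will require descriptive statistics rather than any formal hypothesis testing".

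**The concern.** The objective and the economic section ask for mastery, while the endpoint and the analysis deliver a general quality-of-life total. The protocol has not simply left CRQ scoring open: it names a particular score, and that score is not the one the objective's wording calls for. Elsewhere it asks for sub-scores when it wants them. Section 18.5.4 reports the IPOS overall and by domain, and the EQ-5D-5L by domain. Naming only a total for the CRQ therefore reads as a choice.

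What is at stake is a small piece of design information. Section 6.3.2 says activity outcomes will inform the design of the large-scale trial, and section 15 wants mastery as a possible effect measure. If the analysis is carried out as written, there will be no mean, variability or change for CRQ mastery to use for either purpose.

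**Working it through.** The protocol gives no figure for this point, so there is none to reproduce. The check is a reconciliation of sections, followed by a short calculation of what a total score can show.

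**Step 1. Sections side by side**

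| Section | Role | What the CRQ stands for |
|---|---|---|
| 6.3.2 | Objective | Breathlessness mastery (with mMRC) |
| 15 | Economic outcome | Breathlessness mastery |
| 14 | Instrument | Health-related quality of life, 20 items |
| 16.2.4 | Endpoint | Quality of life |
| 18.5.2 | Analysis | Total score |

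Sections 14, 16.2.4 and 18.5.2 agree with one another. Sections 6.3.2 and 15 agree with one another. The two groups do not meet, and no endpoint or statistical-analysis section contains a CRQ mastery score.

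**Step 2. Does the mMRC fill the gap?** It is named in the same objective and its change to days 14 and 28 is summarised in 18.5.3. But section 14 describes it as the overall level of breathlessness, Appendix A shows a single 0 to 4 grade defined by the exertion that brings breathlessness on, and 16.2.3 files it under safety and toxicity. Section 15 does not mention it in connection with mastery. The CRQ is the only instrument attached to mastery in both places where the word is used.

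**Step 3. Can the total stand in for mastery?** Let k of the 20 equally weighted items be mastery items. Write M for the per-item mean change in those items, O for the per-item mean change in the others, and T for the change in the 20-item mean:

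T = (k/20) × M + (1 − k/20) × O

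T alone does not determine M. With k = 4 as an example, T = 0.10 arises from M = 0.5 and O = 0 (0.2 × 0.5 = 0.10). It arises equally from M = 0 and O = 0.125 (0.8 × 0.125 = 0.10). The same holds for any k below 20.

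**Step 4. Size, under an assumption.** The protocol does not state k. Setting O = 0 and M = 0.5 gives T = 0.5 × k/20:

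| k (assumed) | k/20 | T | Dilution (20/k) |
|---|---|---|---|
| 3 | 0.15 | 0.075 | 6.7-fold |
| 4 | 0.20 | 0.10 | 5-fold |
| 5 | 0.25 | 0.125 | 4-fold |
| 6 | 0.30 | 0.15 | 3.3-fold |

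These are raw-score changes. They do not show a loss of precision, because the SD of a 20-item mean differs from that of a shorter subscale and the protocol gives neither.

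**The case against.** The best case for the plan is that the analysis is right and the label in the objective is loose. The endpoint section calls the CRQ a quality-of-life measure, section 14 describes it that way, and a total score is a natural summary of such an endpoint. The word mastery is attached to the CRQ and mMRC in 6.3.2 but to the CRQ and IPOS in 15, and nowhere does the protocol describe a CRQ mastery subscale. Both tools named in the objective are summarised at the stated days. Section 18.5.2 does not forbid further scores, the section is described as brief, and a fuller SAP is announced. Section 18.5.1 also announces a separate health-economics plan, which could derive a mastery score for section 15.

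Much of this stands. The total does fit the quality-of-life endpoint and should stay. The mismatch could also be closed from the other side, by rewording 6.3.2 and 15 to CRQ quality of life. The SAP or the health-economics plan could supply what is missing.

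What does not fall away is that two sections name mastery as what the CRQ measures, and the sections that define and analyse the endpoint do not carry it through. An SAP that followed 18.5.2 faithfully would not produce it.

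A reader might infer that mastery can never be estimated in this trial. The documents do not support that: the mMRC under the same objective is summarised, and later plans can add a CRQ score.

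**Conclusion.** The objective, endpoint and analysis for the CRQ do not match, and no endpoint or statistical-analysis section specifies a CRQ mastery estimate. This rests on the protocol's own wording and needs no assumption about the instrument. That a total cannot replace a mastery score follows from Step 3 for any subset of the items. The dilution of roughly three- to seven-fold is an illustration only: it assumes 3 to 6 mastery items, equal weights and no change in the remaining items.

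The consequence is modest. A reader might take mastery to be a central construct for the large-scale trial, or take the gap to affect the decision to proceed. Neither is supported. The planned primary outcome of that trial is breathlessness severity at day 28 (6.3.2, 17), the key activity endpoint here is the worst-breathlessness NRS (16.2.2), and the decision rests on recruiting about 60 patients over 12 months (16.1). The CRQ is a secondary measure, summarised descriptively, and enters no sample-size calculation in the protocol.

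**What to change.** - Keep the CRQ total score in 18.5.2 as the summary for the quality-of-life endpoint.
- Add a CRQ mastery score to 16.2.4, stating which items form it and how it is scored, since the protocol does not describe this.
- In 18.5.2, add the mean CRQ mastery score by arm at baseline, day 14 and day 28, with SD, 95% confidence interval and change from baseline.
- Align the CRQ wording in 6.3.2, 15, 16.2.4 and 18.5.2, so that each says whether the total or the mastery score is meant.

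The schedule of events already collects the CRQ at all three time points, so no new data are needed. The cost is a line in the endpoints, a sentence in the analysis and a few table rows: 3 visits × 2 arms = 6 means, and 2 visits × 2 arms = 4 changes. If the sponsor did not intend a mastery score, rewording 6.3.2 and 15 to quality of life would remove the contradiction. Adding the score is preferable because it keeps the stated objective at almost no cost.
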